6.4.5 Follow-up (FU) visits

Every patient will be followed for 3 months after discharge after index treatment.

In line with routine clinical care, at least one personal follow up visit should take place within 3 months of follow up. To ensure comparability of data, in case this follow up visit has not been performed after 3 months (± 2 weeks) in addition a phone call with the patient should provide final information to be documented in the FU visit (phone) of the e-CRF.

At the FU visits the following data from clinical routine will be documented in the e-CRF (if available):

- Patient status
- Relevant concomitant medication and other treatment
- Safety related events: SAEs (including SADEs), AEs of special interest (including ADEs) and DD

Assessments*	Baseline visit	Index-Treatment	FU visits
Informed consent for data use	Х		
In- and Exclusion criteria	Х		
Demographic data	Х		
Medical history	Х		
Patient's status	Х		X**
Medication/other treatment	Х	X	X**
Concomitant diseases	Х		
Data regarding index treatment and related therapy		X	
Outcome of index treatment		X	
Safety related events (SAEs, SADEs, ADEs, DD)		X	Х

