6.4.3 Screening and baseline/enrolment visit (day 1 of observation)

Patients will be screened and enrolled by contracted study sites only, i.e. expert centres. Screening of potentially eligible patients will be performed within routine clinical care. Check for eligibility according to in- and exclusion criteria will be performed using routine clinical care data.

Potentially eligible patients will be informed about the use of their medical data in the study. The patient will be given sufficient time to consider the implications of data use before deciding whether to consent. Participation in this study means following clinical routine care procedures, but allowing for documentation of medical data in a central web-based data base (e-CRF). If the patient is willing to agree, the informed consent form for data use will be provided for signature. As soon as signed informed consent is available, the patient has been enrolled into the study.

Informed consent for use of personal medical data will often be given after the date of index treatment because the treatment is performed in routine clinical care. The fact of enrolment and the enrolment date will in any way be documented within the baseline visit. After signing the consent, patients are checked for eligibility according to in- and exclusion criteria by the participating sites consecutively to minimise selection bias. Study relevant data will be reported in the e-CRF. The e-CRF system will automatically display the patient ID as consecutive number across all participating study sites, i.e. without reference to the recruiting site.

The following data items will be documented of each participating patient at enrolment:

- Demographic data
- Patient's physical status
- Medical history
- Relevant concomitant medication and diseases

Data on the entire clinical stay for treatment of the index defect will be documented.

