6.4.4 Treatment of the index defect

The decision of treatment of the index defect lies with the treating physician in routine clinical care. Indication as well as initiation of treatment should follow applicable medical guidelines, local clinical care policy and the IFUs of the devices used.

Initiation of treatment might start as routine clinical care procedure before enrolment into the study (i.e. informed consent of the patient) but data can be entered into the e-CRF after signed informed consent is available (i.e. after enrolment), only.

- Primary EV therapy is defined as the utilisation of EVT as first-line therapy for perforation or leak.
- **Rescue EV therapy** is defined as EVT placement following failure of definitive surgical repair for a perforation or leak.
- **Defect closure following EVT placement** is defined as 1) no evidence of continued leak under direct endoscopic visualization and 2) a negative oesophagram following discontinuation of EVT therapy.

Data regarding index defect, related therapy and outcome following EVT placement will be documented in the e-CRF at the Index-treatment visit.

The following data items will be documented of each participating patient at the index-treatment visit:

- Data of index treatment and related therapy (defect size, type and location of perforation, pre-existing pathology, ASA-classification, Perforation Severity Score (PSS), primary or rescue EVT application, type of endo-sponge placement, type of surgical repair, time to placement of EVT following diagnosis, number of EVT changes, number of days between EVT changes, total length of EVT therapy, relevant laboratory parameters)
- Outcome of index treatment (including 30-day mortality, closure interventions following treatment of index defect, hospital length of stay (LOS), ICU LOS, EVT therapy-specific findings (e.g. migration, dislodgement, erosion), time to oral diet initiation / endoscopic release for stoma relocation following successful defect closure).

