6.4.6 Visit table

* If data are available in routine clinical care.

** Only if the FU-Visit is performed on site

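### No follow-up contact is assigned the primary-endpoint release, so releases after discharge may be missed

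*Protocol*

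**What the plan says.** The primary endpoint (Protocol 5.2.1 and 6.1.3.1) is the time from first use of the device to release for oral food intake, or to endoscopic release for stoma relocation in lower-GI use. Lower-GI patients without a stoma use the oral-intake endpoint.

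- **Where release is recorded.** Section 6.4.4 says that data on "outcome following EVT placement will be documented in the e-CRF at the Index-treatment visit". Among the outcome items is "time to oral diet initiation / endoscopic release for stoma relocation following successful defect closure". The visit table (6.4.6) ticks the outcome row for index treatment only.
- **What follow-up records.** Section 6.4.5 states "Every patient will be followed for 3 months after discharge after index treatment". Its list begins "At the FU visits the following data from clinical routine will be documented in the e-CRF (if available" and names patient status, medication or other treatment, and safety-related events.
- **What the phone call records.** If no personal visit took place at three months (± 2 weeks), "a phone call with the patient should provide final information to be documented in the FU visit (phone) of the e-CRF". In the visit table, status and medication carry the footnote "Only if the FU-Visit is performed on site", so a phone contact keeps only the safety row.

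**The concern.** The protocol sets out its own collection schedule, and that schedule gives the primary endpoint no contact after the index-treatment record. A site that follows the list and the table literally has no prompt to ask about release at a follow-up visit or by phone.

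This matters most for lower-GI patients with a stoma. The planning source in 6.3.7 puts stoma relocation at a median of 4 months (interquartile range 3 to 6) in the vacuum-therapy group, so many releases can be expected after discharge. Upper-GI patients, and lower-GI patients without a stoma, are probably less affected because oral intake tends to resume sooner.

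The confirmatory analysis (section 7) is a one-sample log-rank test of observed against expected events. Each unrecorded release is a lost event.

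**Working it through.** **Setting the passages side by side**

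| Item | Index-treatment record | On-site follow-up | Phone follow-up |
|---|---|---|---|
| Release (within outcome of index treatment) | ticked | blank | blank |
| Patient status, medication | medication only | ticked | excluded by footnote |
| Safety events | ticked | ticked | ticked |

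Patient status might carry a release at an on-site visit, but it is not defined that way. No sentence says that the outcome record is updated to the end of follow-up.

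**Effect of one missed release on the test**

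Let λ0 be the control hazard, t the true release time and c the end of follow-up. Correctly recorded, the patient adds 1 to O and λ0·t to E. If the release is missed and the patient stays at risk to c, the patient adds 0 to O and λ0·c to E. O − E therefore falls by 1 + λ0·(c − t). Superiority needs O above E, so under this handling the bias is against superiority.

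**Illustration of how many stoma releases fall after discharge**

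The protocol gives no figure for this share, so there is none to reproduce. Inputs:

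- 75% relocated at 6 months with vacuum therapy, exponential times (6.3.7): λ1 = −ln(0.25)/6 = 0.2310 per month. Check: 1 − exp(−6 × 0.2310) = 0.75.
- Follow-up to discharge + 3 months (6.4.5).
- Stay from index use to discharge: not given. Assumed 14, 37 and 60 days, at 30.44 days per month. The 37 days is an average from five patients in a rectal series cited in 3.2.
- Lower-GI patients with a stoma: 110/2 (about equal balance, 6.3) × 0.764 diverted (pooled figure in 3.2) = 42.

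With F(x) = 1 − exp(−λ1·x), d = discharge and c = d + 3 months, the share after discharge is [F(c) − F(d)]/F(c).

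| Assumed stay | F(d) | F(c) | Share after discharge | Patients, 42 × [F(c) − F(d)] |
|---|---|---|---|---|
| 14 days | 0.101 | 0.550 | 82% | 18.9 |
| 37 days | 0.245 | 0.622 | 61% | 15.9 |
| 60 days | 0.366 | 0.683 | 46% | 13.3 |

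Three cautions apply:

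- The exponential gives F(3 months) = 0.50, whereas the source's lower quartile implies 0.25. Reading the source quartiles as straight lines through (0, 0), (3, 0.25), (4, 0.50) and (6, 0.75) gives 89%, 81% and 74% instead.
- These are relocation times. Endoscopic release comes before relocation, which pulls the share down by an unknown amount.
- The calculation takes 75% as released, as 6.3.7 words it. The 13 expected events stated there fit 75% taken as not released: 99 × (1 − 0.75^0.5) = 13.3, against 99 × (1 − 0.25^0.5) = 49.5 if released. That discrepancy is a separate matter.

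The table shows how many releases are exposed to the gap. It does not show how many would be lost.

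**The case against.** The strongest reply is that the endpoint does have a home. Section 6.4.4 requests release for every participant, beside 30-day mortality and lengths of stay, none of which can be entered on a treatment day. Consent is mostly expected after treatment (6.1.6, 6.3.4), and entry is barred before it. The index-treatment visit is therefore a record and not a date. Section 6.1.4 has later routine-visit data reported, and 8.3 allows tracked changes. A tick shows which form holds an item, not when the form closes.

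Most of this stands. A reader might infer that releases after discharge will not be collected; the protocol does not support that. What remains is that no text keeps the form open to three months after discharge or names the contact that asks. Thirty-day mortality does not reach that far.

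Two further readings go too far:

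- Section 6.4.3 says "Data on the entire clinical stay for treatment of the index defect will be documented". This states what is included; it does not end documentation at discharge.
- The phone sentence and the footnote are not opposed rules. The closing information is undefined, and final safety data would satisfy it. This is an unresolved ambiguity.

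It is also fair that releases after follow-up ends are lost whatever the table ticks. That concerns the length of follow-up, and the shares above exclude them.

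**Conclusion.** The point holds as a gap in the stated schedule and should be fixed. Releases after discharge may be missed, mainly in about 42 of 110 patients (lower GI with a stoma). The consequence is fewer events and less power. If unrecorded patients stay at risk to the end of follow-up, the test is also biased against superiority. The direction under other handling, such as leaving out patients with no recorded time, is not shown here, so neither a false-positive risk nor its absence should be claimed in general.

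The amount lost cannot be derived from the document; it depends on e-CRF prompts that are not shown. The 46% to 82% is an illustration resting on assumed stays, the planning exponential, and relocation standing in for release. A reader might go on to infer a distorted observed-to-expected ratio for the trial. That would need a capture rate the protocol does not give, and the analysis pools these patients with the others.

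A separate minor point: 6.4.4 ties the release item to successful defect closure, whose definition includes "a negative oesophagram following discontinuation of EVT therapy". The endpoint in 5.2.1 and 6.1.3.1 carries no such condition, and an oesophagram does not apply to a rectal defect.

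**What to change.** In 6.4.5 and 6.4.6:

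- Add to every follow-up contact, including the phone call, the release status and date for the applicable endpoint, or the date last known without release. Confirm endoscopic release from site records where available.
- Tick this row under follow-up without the on-site restriction.
- State that the index-treatment outcome form is updated to the end of follow-up.
- Say what the phone call must record, and reconcile that with the footnote.

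Separately, reconcile the closure condition and its oesophagram element in 6.4.4 with the endpoint definition and with rectal defects.

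The cost is two e-CRF fields at contacts that already exist, one table row, one or two sentences, and a small documentation burden for sites. No visit or procedure is added, so the study stays observational.

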6.4.6 Visit table

* If data are available in routine clinical care.

** Only if the FU-Visit is performed on site

6.4.7 Activities performed by sponsor representatives (excluding monitoring)

The sponsor will define potentially eligible hospitals and physicians for participation in this study based on his knowledge on their training and expertise in use of the Endoscopic (Endoluminal) Vacuum Therapy in the gastrointestinal tract treatment in routine clinical care. Eligibility of each study site according to standards following ISO 14155:2020 will be assessed and documented by the responsible CRO.

No other activities of sponsor representatives related to this study will be performed.

6.4.8 Known or foreseeable factors that may compromise the outcome of the study or the interpretation of results

This clinical study is purely observational. All procedures and therapies are representing routine clinical care based on individual decisions by the treating physician and are not given as standardised procedures in the study protocol. It is expected that observed variations in diagnosis and treatment of defects of interest will be further compared to controlled clinical trials with given standards. Selection bias will be controlled by means of data collected about the site itself and pooled details about their patients of interest in routine clinical care.

The data of this study represent routine clinical care of patients with acute defects, injuries and wounds in the oesophagus or rectum, including perforations (iatrogenic or spontaneous) and anastomotic insufficiencies without limitations normally given by protocol definitions of controlled clinical trials. Thus, the generalizability of results is deemed to be higher compared to those of controlled clinical trials. However, due to the expected larger range of variations in procedures and therapies the level of statistical significance is expected to be lower but allowing for generation of hypotheses which might be investigated in subsequent clinical research projects.

6.5 Monitoring plan

No routine onsite monitoring is initially planned within this non-interventional, observational study. Since only observation of routine clinical care without any protocol-defined interventions will be performed, the safety and well-being of study patients is the scope of routine clinical care. Thus, onsite monitoring could be justified for double-check of completeness and quality of data, only. Data quality will primarily be controlled by means of statistical checks on data available for all study sites allowing to detect outliers, extremes and deviation in distribution of data. In case of suspicious findings, on-site visits in corresponding sites might be performed.

7. Statistical considerations

In this observational study the time period from index therapy to release for oral food intake (in upper GI tract use) or endoscopic release for stoma relocation (in lower GI tract use) will be compared to published historic controls. For this, the time period is compared to published data of other EVAC and conventionally managed therapy, especially data from Wasmann et al. [29]. In addition, after half of the patients with complete follow-up, an interim analysis will be performed and sample size will be recalculated. It is expected that until then the results of a randomized clinical trial comparing an EVAC therapy to standard minimally invasive oesophagectomy (refer to NCT04162860 and [22]) will be available for adaptation of assumed confidence intervals and sample size (see 6.3.7). The hypothesis of superiority against conventionally managed therapy will be tested confirmatory.

For primary analysis a one-sample log-rank test will be used, comparing the observed number of events to the expected number of events of the control groups. The two-sided type-one error is 0.54% for the interim analysis and 4.92% for the final analysis.

Data from all study sites will be pooled for analysis. Standard statistical methods will be used to analyse all data. Continuous variables will be summarized using the number of observations, mean, median, standard deviation, minimum and maximum values. Categorical variables will be summarized using the number of observations and percentages.

A separate Statistical Analysis Plan will be prepared prior to the start of data analysis, detailing the statistical analyses methods that will be used.

8. Data management

Study and site management as well as data cleaning, data management and statistical analysis was delegated by the sponsor to CRI – The Clinical Research Institute, Munich, Germany, as responsible Contract Research Organisation.

Applicable national and international legal requirements for data handling and data archiving will be met. Clinical data will be collected using the web-based MARVIN system, a GCP and 21 Code of Federal Regulations (CFR) 11 compliant Electronic Data Capture (EDC) and Clinical Trial Management System (CTMS) software based on Clinical Data Interchange Standards Consortium (CDISC) data standards. Medical data within this study will be recorded directly in the e-CRF at the site without use of paper documents. The e-CRF system is available for all participants in the study 24 hours/7 days during the course of the study. Before closure of the study, all participating sites will be provided media with PDFs of all e-CRF data ever entered in the corresponding site together with all related metadata (e. g. audit trail, data queries).

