6.3.6 Expected duration of each subject's participation

The mean follow-up period (from date of enrolment to end of follow-up) of all patients is expected to be about 3 months.

6.3.7 Number of subjects required to be included in the study

As discussed in 3.2, the evidence for the different treatment options is very limited. Especially the patient populations, e.g. regarding underlying diseases, as well as the processes in the therapy are very different in the individual studies published. Therefore a reasonable sample size calculation is not possible at the moment. Thus, an interim analysis with sample size re-calculation is planned.

The best evidence for an **initial sample size calculation** is provided by data of the study by Wasmann et al. [29], a cohort study including 334 patients with ileal defects, where EVAC therapy was compared to conventional management of defect treatment. The median time to stoma relocation was estimated as 4 months in the EVAC group (interquartile range 3 to 6 months) versus 4 months (3 to 13 months) in the conventional management group. Therefore, the proportion of patients with stoma relocation after 6 months is known as 75% in the EVAC group. Assuming a constant increasing proportion in the conventional management group from 4 to 13 months with 2.8% per month, a proportion of 56% stoma relocations after 6 months is expected for the conventional group. Even if the follow-up is set to 3 months in this study, sample size calculation can be based on 6 months results.

Sample size calculation was performed with PASS 16.0.3 using a two-sided, one-sample log rank test. A group sequential design with the alpha spending function of O'Brien-Fleming results in a two-sided type one error of 4.92% for the final analysis. A sample size of 99 analysable subjects achieves 80% power to detect shorter time to release for food intake or endoscopic release for stoma relocation (assuming a proportion of relocated stoma of 75% after 6 months in the EVAC group when the proportion in the historic control group is 56%). The expected number of events during the study with 3 months of follow-up is 13. It is assumed that the survival time distributions of both groups are approximated reasonable well by the Weibull distribution with a shape parameter of 1.00. To account for treatment switching and early drop-outs of 10%, 110 analysable patients will be enrolled.

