After data of complete follow-up of about half of the enrolled patients are available, an interim analysis will be performed and sample size will be recalculated. It is expected that until then the results of an ongoing randomized clinical trial comparing EVAC therapy to standard minimally invasive esophagectomy (refer to NCT04162860 and [22]) are available and can also be used as more reliable assumptions for sample size recalculation. The maximum sample size is set to 1.5 times the initial sample size, equal to 165 patients.

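### The printed significance levels of 0.54% (interim) and 4.92% (final) do not come from the O'Brien-Fleming spending function that the protocol names, and together they spend about 5.13%

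*Protocol*

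**What the plan says.** Section 6.3.7 of the protocol bases the sample size on a two-sided one-sample log-rank test with one interim look, and states: "A group sequential design with the alpha spending function of O'Brien-Fleming results in a two-sided type one error of 4.92% for the final analysis". Section 7 gives both thresholds: "The two-sided type-one error is 0.54% for the interim analysis and 4.92% for the final analysis".

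The timing of the interim appears twice. Section 6.3.7 says: "After data of complete follow-up of about half of the enrolled patients are available, an interim analysis will be performed". Section 7 says: "after half of the patients with complete follow-up, an interim analysis will be performed and sample size will be recalculated". Neither section gives another information fraction, and neither prints the overall type I error.

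Section 7 also sets the status of the test: "The hypothesis of superiority against conventionally managed therapy will be tested confirmatory".

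**The concern.** For a two-look design, the spending function, the overall level and the information fraction at the interim together determine both nominal levels. The protocol names the function, implies an information fraction of about one half and prints both levels. The levels should therefore follow from the first two once an overall level is assumed, and they do not.

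Two things are at stake. First, the thresholds of a test described as confirmatory are credited to a method that does not produce them. An interim p-value between 0.305% and 0.54% would be significant by the levels in section 7 and not significant by the function named in section 6.3.7. That has to be settled before interim data are seen. Second, if the intended overall level is 5% two-sided, the printed pair exceeds it slightly at the planned interim.

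**Working it through.** **Inputs.** Printed levels of 0.54% and 4.92%, two-sided (section 7); O'Brien-Fleming alpha spending function (section 6.3.7); information fraction t = 0.5, from the interim at about half of the patients (sections 6.3.7 and 7). Assumption: overall two-sided level of 5%. Because patients with partial follow-up could raise t, a range is shown.

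**1. Levels from the named function.** The two-sided error spent at t is 4·[1 − Φ(z/√t)], with z = Φ⁻¹(1 − 0.05/4) = 2.2414. At t = 0.5, z/√t = 3.170 and the interim level is 0.305%. The final level makes P(|Z1| > c1 or |Z2| > c2) = 5%, where Z1 and Z2 are bivariate normal with correlation √t. This gives 4.90%.

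| t | interim | final |
|---|---|---|
| 0.40 | 0.079% | 4.97% |
| 0.48 | 0.243% | 4.92% |
| 0.50 | 0.305% | 4.90% |
| 0.55 | 0.502% | 4.84% |
| 0.558 | 0.54% | 4.83% |
| 0.60 | 0.762% | 4.76% |

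The printed final level fits t = 0.480 and the printed interim level fits t = 0.558. No single row gives both.

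**2. Other readings at t = 0.5.**

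- Spending form 2 − 2Φ applied to the whole 5%: 0.557% / 4.78%.
- One-sided 5% spending: 0.557% / 4.82%.
- Classical O'Brien-Fleming boundary (constant 1.977): 0.517% / 4.80%.

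None gives 0.54% / 4.92%.

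**3. Does the assumed 5% cause the mismatch?** Let the overall level vary at t = 0.5. Matching 4.92% needs an overall 5.02%, and the interim is then 0.307%. Matching 0.54% needs about 6.8%. With t and the overall level both free, the pair fits only near t = 0.555 with an overall level of 5.09%, which is above 5% and not at one half.

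**4. Joint error of the printed pair.** 0.54% corresponds to |z| = 2.782 and 4.92% to |z| = 1.967. P(|Z1| > 2.782 or |Z2| > 1.967) is:

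| t | 0.40 | 0.50 | 0.55 | 0.60 | 0.70 |
|---|---|---|---|---|---|
| two-sided error | 5.20% | 5.13% | 5.10% | 5.06% | 5.00% |

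At t = 0.5 the share in the benefit direction is 2.56%. Rounding of the printed levels (0.535–0.545% and 4.915–4.925%) moves the total only between 5.12% and 5.14%. To hold 5% at t = 0.5, a final level of 4.92% allows an interim level of at most 0.258%, and an interim level of 0.54% allows a final level of at most 4.79%.

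**5. Shape.** 2.782 / 1.967 is about 1.414, or √2. This is the classical O'Brien-Fleming shape for a look at half the information, but the constant is 1.967 where 5% needs 1.977.

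**The case against.** The strongest reply is that this has almost no consequence. The overall 5% is not printed, so the excess depends on an assumption. It is 0.13 points two-sided and about 0.06 in the benefit direction, and smaller still if partly followed patients push the information fraction to 0.55–0.60. The final levels differ by only 0.02 points. The √2 ratio suggests that a classical boundary was meant and that the words about alpha spending are the loose part. A later SAP can settle the operational thresholds.

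The normal approximation also matters more than the boundary. A null simulation (99 patients, 49 of them at the interim, exponential times with 56% of events by 6 months, 3 months' follow-up, statistic (O − E)/√E, 300,000 runs) gave 5.25% for the printed pair and 5.11% for each replacement pair. Changing the pair does not by itself bring the real error to 5%.

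Most of this stands, and it limits the point to a minor one. It does not remove the mismatch. The printed levels differ from the named function whatever overall level is assumed at half information, and they also differ from the classical boundary at 5%. A SAP would still inherit two conflicting instructions, and the protocol itself has fixed these numbers.

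**Conclusion.** The point holds, as a minor error. The levels in section 7 are not the output of the function named in section 6.3.7. The main gap is at the interim: 0.54% against 0.305%, a factor of 1.77. At half information the printed pair spends 5.13% two-sided, and it reaches 5.00% only near 70% information, well beyond the planned half.

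The 5.13% rests on the normal approximation and a fraction of one half. Calling it an excess rests on an intended 5%. The mismatch itself does not depend on the size of that excess, and no study conclusion is likely to turn on the excess alone.

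**What to change.** State the overall two-sided level of 5% and make sections 6.3.7 and 7 agree on one method and one pair of levels. There are two options:

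- Keep the O'Brien-Fleming spending function and print 0.305% (interim) and 4.90% (final) for half information, with both recomputed at the actual information fraction.
- Use the classical O'Brien-Fleming boundary, print 0.517% and 4.80%, and remove the reference to an alpha spending function.

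The cost is wording in two sections. With the effect that gives 80.0% power under the printed pair (drift 2.802, t = 0.5), power becomes 79.9% with the first option and 79.7% with the second. The chance of crossing for benefit at the interim goes from 21.2% to 16.3% or 20.7%.
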